#### 7.5. TERMINATION CRITERIA FOR PERFORMING PROFESSIONALS

All professionals included in the study are free to withdraw their consent to participate in the study, in whole or in part, at any time and without giving reasons. In such a case, professionals will be asked to state the reason for discontinuation but will be informed that they are not required to do so. Time and reasons for withdrawal (if given) will be documented. Professionals may be excluded from the study if a violation of inclusion or exclusion criteria is subsequently identified or if data collection is incomplete.

#### 7.6. TERMINATION CRITERIA FOR THE ENTIRE STUDY

Termination of the study is not foreseen in general. An interim evaluation is not planned for short study durations.

If less than half of the patients have been recruited after three months, an interim evaluation will take place. The study can be discontinued if the interim evaluation shows that the recruitment rate is not sufficient to achieve the objectives mentioned under 4. as the number of patients is too low and an increase in the recruitment rate is not possible.

The decision to discontinue the study is made by the project management together with the study physicians. All patients included in the study up to the point of discontinuation should be evaluated in any case in order to be able to evaluate the early mobilization in this patient group, the previous implementation and the experience of the mobilizing specialists.

## 8. METHOD AND PROCEDURE

Patients of the LMU Hospital will be included according to the inclusion and exclusion criteria (see 5.2. and 5.3.). All patients who are to be treated surgically and whose postoperative care is planned in the anesthesiological intensive care units will be screened according to the inclusion and exclusion criteria. If the expected duration of postoperative ventilation exceeds 48 hours and there are no contraindications, the patient is given an information session. This should be done preoperatively with awake patients who are able of giving consent. In case of consent, the patient will be included in the study.

In addition, within the scope of the experience of the mobilizing specialists, nurses, physiotherapists, and physicians will be included according to inclusion and exclusion criteria, who are predominantly assigned to the intensive care units of the LMU Hospital and from T2 onwards to the anesthesiological intensive care units.

With the start of robot-assisted early mobilization, the survey will be conducted within the framework of organizational feasibility. This is carried out by project staff and ward staff. The survey ends with the last robot-assisted mobilization.

[figure not shown]

Fig. 5: Detailed procedure of the study with examination times of the patients

All patients will receive a physical examination at different time points to assess physical functionality and muscle strength, as well as a sonographic examination of leg muscles, diaphragm, and lungs. These examinations should be performed on day -1 (preoperatively), on postoperative days 1,2,3, then once a week if the patient remains in the Intensive Care Unit, on day 28, on the day of discharge from the Intensive Care Unit, and on a follow-up examination approximately 3 months after discharge from the Intensive Care Unit. The follow-up examination should only take place if the patients present themselves at the LMU Hospital anyway due to medically indicated follow-up examinations (not study-related). Alternatively, patients can be asked about their condition by telephone (see Fig. 5).

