## 4.3 EVALUATION OF THE EFFECTS ON PATIENT OUTCOMES

- Can robot-assisted early mobilization improve muscle strength and reduce muscle loss compared with the historical collective?
- Can robot-assisted early mobilization reduce the duration of ventilation?  
In addition, further questions will be addressed:
- Does robotic-assisted early mobilization result in changes in consciousness, pain, cognition, health perception, cardiocirculatory and respiratory function, other factors such as pressure ulcers, bowel emptying, insulin requirements, and duration of treatment?

For this purpose, the following outcome criteria of the patients are examined.

Primary outcome criteria	Physical function/muscle strength	Surveyed according to the MRC (Medical Research Council) classification on upper and lower extremity and using the FSS-ICU (32, 33) at discharge ICU.
	Parameters for the assessment of muscle deterioration	Muscle thickness of quadriceps femoris muscle (thickness quadriceps femoris muscle and cross sectional area rectus femoris muscle)  Muscle thickness of the diaphragm / Thickening fraction diaphragm  Diaphragm mobility at discharge ICU
	Ventilation time	Duration (d) of invasive ventilation

Secondary outcome criteria	Consciousness/ cognition/ pain/ health perception	Pain using the Visual Analog Scale (VAS) (before and after mobilization).  Delirium incidence using the CAM ICU (34): number of days without delirium.  Sedation level using the Richmond Agitation Sedation Scale (RASS)(35)  level of consciousness using the Glasgow Coma Scale (GCS) (36)  Health-related quality of life after 3 months using the SF-36 questionnaire (37)
	Hemodynamics	Blood pressure / catecholamine demand / heart rate / cardiac output / oxygen consumption
	Respiration	CPAx-respiratory function(38) / oxygenation index / lung ultrasound parameter
	Others	Intestinal evacuation (yes/no)  Decubitus (grade classification 1-4 according to Shea (39))  Lactate level before and after mobilization (if laboratory value available)  Insulin requirement
	ICU Scores	SOFA [39] / Apache II (40) / SAPS II (41)  Intensive care unit treatment duration / inpatient treatment duration

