#### Conventional early mobilization

The comparison group is a historical collective, which also meets the inclusion and exclusion criteria of the study. These patients were early mobilized following the ward routine of the intensive care units conventional early mobilization according to the instructions of the treatment team, consisting of physicians, nurses, and physiotherapists. Conventional early mobilization cannot be precisely defined on the basis of a retrospective study (45, 15). The information used for the study regarding early mobilization and the defined outcome criteria of the patients is taken from the routinely collected data.

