### 8.3. DATA COLLECTION EFFECTS ON PATIENT OUTCOMES

In this study, various interventions will be performed on patients. All invasive procedures performed on patients will be performed as routine procedures independently of the study in the Intensive Care Unit (ICU) according to medical indication. The following study-related procedures will be performed on the patients beyond the informed consent and documentation of patient-related data:

Patients will receive robot-assisted mobilization within the first 72 hours after admission to the Intensive Care Unit  $\geq 2$  x / day for 20 minutes, for a minimum of ten treatment cycles or seven days. Clinical-functional examination with collection of clinical scores and ultrasound parameters on day -1, 1,2,3, then once a week if continued in the Intensive Care Unit, day 28, day of discharge from the Intensive Care Unit, 3 months after study inclusion (within the data collection period) (39).

No other study-related burdens or risks arise for patients.

An overview of clinical and study-related measures is provided below:

Measure	Measure performed	Specification/ Invasiveness
Education and informed consent	Study-related	Noninvasive
Clinical examination to determine physical function	Study-related	Noninvasive

Sonographic examination of the lungs, diaphragm, and M. quadriceps femoris	Study-related	Noninvasive
Early mobilization, robot-assisted	Study-related	Non-invasive within the framework of the CE-certified indication for approval
Documentation of patient-related data	Study-related	Noninvasive

In addition, personal data, laboratory values from clinical routine and clinical data are recorded:

Domain	Parameters
1. Personal Data	
	Age, sex, height, weight
Diagnosis	Admission and progressive diagnoses
Therapy	Medications, infusion solutions
2. Laboratory diagnostic data	
	Parameters determined from the routine
3. Clinical data	
SOFA score (52) Apache II score (41) SAPS II score (40) RASS(31) VAS GCS (36) Decubitus score according to Shea (37)	Temperature, mean arterial pressure, heart rate, respiratory rate, Oxygenation index, Blood pH, Lactate, Bicarbonate, Operative status, Glasgow Coma Score Chronic conditions, export urine See Scores
Acute renal failure	AKIN-Stadium
Data Organ replacement	Renal replacement procedures, ECMO therapy
Advanced hemodynamic monitoring	Cardiac index, zvO2... (if advanced hemodynamic monitoring such as pulmonary catheter or PICCO is established)

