### *Clinical examination to determine physical function/ health-related quality of life.*

To assess physical function and muscle strength, the following non-invasive examinations will be performed and/or scores will be collected as required by the study:

FSS-ICU (53): the FSS-ICU assesses the patients "Physical Performance" based on 5 factors. For each of the 5 tasks, a minimum of 0 to a maximum of 7 points can be assigned. The following table summarizes the individual tasks.

Task	Score
1. Turning	
2. Transition from lying to sitting	
3. Transition from sitting to standing	
4. Sitting at the edge of the bed	
5. Walking	
Total score	

MRC (Medical Research Council) classification on upper and lower extremity:

Assessment of the degree of strength using the MRC classification is widely used and follows the well-known classification (see table below):

	Degree of Strength
Absence of muscle contraction	0
Visible muscle contraction	1
Movement with elimination of gravity	2
Active movement against gravity	3
Active movement against resistance	4
Normal force	5

At the follow-up examination approximately 3 months after discharge from the intensive care unit, the health-related quality of life will also be assessed using the SF-36 questionnaire (34).

*Sonographic examination of the lungs, diaphragm and Musculus quadriceps femoris*

Part of the examination is the sonographic evaluation of the diaphragm, lungs and Musculus quadriceps femoris.

These will be briefly illustrated with reference to Figures 6-8.

[figure not shown]

Figure 6: Landing points sonography lung: quantification of diaphragm thickness is performed on the right side of the body, where the diaphragm approaches the thoracic wall in the region of the liver (so-called apposition zone) (38, 54).

To determine the thickening fraction, the diaphragm thickness is determined in inspiration and in expiration (55).

[figure not shown]

Fig. 7: Assessment of diaphragmatic excursions: Using a submammary plumb line (left image), the liver is first visited on the right side of the body as a sonic window (middle image). The diaphragmatic excursions are quantified using the M-mode (right image). On the left side of the body, the spleen is used as a sonic window (not shown).

The Musculus quadriceps femoris will be quantified using cross sectional area and thickness (56, 57). The principle of the examination is shown in Figure 8.

[figure not shown]

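### As written, the 3-month SF-36 may come only from patients with another medical reason to attend this hospital and enough of the data collection period left

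*Protocol*

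**What the plan says.** Section 4.3 asks: "Does robotic-assisted early mobilization result in changes in consciousness, pain, cognition, health perception" and so on through a list of further outcomes. The matching secondary criterion is "Health-related quality of life after 3 months using the SF-36 questionnaire".

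The questionnaire is scheduled in section 8.3, in the subsection on clinical examination and quality of life. There, at the follow-up examination about three months after ICU discharge, "the health-related quality of life will also be assessed using the SF-36 questionnaire".

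Section 8 sets the condition for that examination: "The follow-up examination should only take place if the patients present themselves at the LMU Hospital anyway due to medically indicated follow-up examinations". The next sentence gives the alternative: "Alternatively, patients can be asked about their condition by telephone". It refers to Fig. 5, which is not shown in the text at hand.

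The opening of section 8.3 times the last examination differently: "3 months after study inclusion (within the data collection period". The robot-assisted mobilization paragraph of section 8 also counts three months from inclusion, and lets a patient's participation end when the study's recording period ends. Section 5 plans five to six months of data collection.

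For the historical group, section 8 (conventional early mobilization) says that the information on the defined outcomes "is taken from the routinely collected data".

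**The concern.** Whether a patient completes the SF-36 can depend on two things that are not under study. The first is having a separate medical reason to come back to this particular hospital. That is plausibly related to health, which is what the SF-36 measures, and to where the patient is followed up. The second is being enrolled early enough for three months to pass before data collection closes.

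The SF-36 is the protocol's only stated measure of quality of life after the ICU stay. If it is obtained in an undefined subset, its mean describes that subset and not the survivors of the intervention group. A reader of the results could not tell how far the two differ unless survivors, contacts and completed questionnaires are counted.

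**Working it through.** No stated figure is in dispute on the first point, so the passages are set side by side. The cut-off can be checked by arithmetic.

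**1. What the text guarantees for a patient who does not return**

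- In-person examination: none, because section 8 makes it conditional on a medically indicated visit.
- Telephone contact: possible but not required, since section 8 says only that patients can be asked.
- SF-36 by telephone: not stated. Section 8 gives the content of the call as the patient's condition. The only place that schedules the SF-36 (section 8.3) is the examination itself.

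A team that follows the text exactly could therefore hold no SF-36 for any patient who does not return.

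**2. Where the window comes from**

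Inputs from section 7.3: 30 to 35 intervention patients, 6 to 8 recruited per month, expected duration five to six months.

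- At 6 per month: 30/6 = 5.0 months and 35/6 = 5.8 months. This reproduces the stated duration.
- At 8 per month: 30/8 = 3.75 months and 35/8 = 4.4 months.

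The planned duration equals recruitment time at the lower rate. It leaves no added time for a 3-month follow-up of late recruits.

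**3. Share of patients with three months left inside the window**

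Assumption: accrual is even over the whole window of T months, and the three months run from inclusion. Share = (T − 3)/T.

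| T (months) | Share | Of 30 | Of 35 |
|---|---|---|---|
| 5 | 2/5 = 40% | 12 | 14 |
| 6 | 3/6 = 50% | 15 | 17.5 |

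These are upper limits, before any death, refusal or non-return. Counting from ICU discharge lowers them further. The protocol gives no expected ICU stay, so by how much cannot be said.

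**4. Sensitivity to the accrual assumption (30 patients)**

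- Recruitment at 8 per month with the window still open for 5 or 6 months: 8 × (5 − 3) = 16 and 8 × (6 − 3) = 24, that is 53% and 80%.
- Recruitment at 8 per month with the window closing at the last enrolment (section 7.3 regards the study as complete once the number is recruited): 8 × (3.75 − 3) = 6, that is 20%.

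The share moves a good deal with the reading, but none of these readings gives every patient three months.

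**5. Precision of what remains**

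The half-width of a 95% confidence interval for a mean, in SD units, is 1.96/√n (normal approximation). For n = 30 it is 0.36 and for n = 12 it is 0.57.

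**6. Comparator**

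Historical outcomes come from routine records, and no source of SF-36 data is named for that group. The protocol therefore states no between-group contrast on the SF-36 that could be computed, however complete the intervention group's data are.

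**The case against.** The strongest reply is that the protocol does provide for patients who do not return. The telephone sentence follows directly on the restriction. Section 4.3 defines the SF-36 outcome without requiring a visit, and the missing Fig. 5 may show the SF-36 at that contact. Avoiding study-only visits is also a reasonable way to limit burden in a small study with a feasibility focus. All of this stands. It means that restriction of the SF-36 to returning patients is a risk left open by the text, not an established fact.

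Three stronger readings are tempting, and the documents do not support them.

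- A reader might infer that the health-perception question fails because there is no preoperative SF-36. But that question sits in a list with pressure ulcers and duration of treatment, and sections 3 and 6 frame the study as a comparison with conventional mobilization. A between-group comparison of 3-month status needs no baseline. What is missing is a comparator source. Change from day -1 in the robotic group alone would mix surgery, illness and recovery with any effect of the device.
- A reader might infer that the same selection damages the strength and ultrasound outcomes. Section 4.3 sets those at ICU discharge. Only the additional 3-month values, which are not defined outcomes, are confined to attenders.
- A reader might want a bias in SF-36 points. The protocol gives no attendance, no survival and no expected difference between attenders and others, so any such figure would be invented.

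**Conclusion.** The point holds as a weakness in how one secondary outcome is collected. The rule for the 3-month examination ties the SF-36 to medical need at this hospital. The telephone route does not clearly replace it, and the end of data collection removes late recruits. Under even accrual over the planned window, 40% to 50% of patients can reach three months inside it; other readings of section 7.3 range from 20% to 80%. The size and direction of the selection bias cannot be derived from the protocol.

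The 3-month anchor is also inconsistent: ICU discharge in two places, study inclusion in two others. This must be settled whatever else is done.

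The primary outcomes (strength and function, muscle and diaphragm measures at ICU discharge, ventilation time) are untouched. The change is worth making because it is cheap, not because the main comparison depends on it.

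**What to change.** In sections 8 and 8.3:

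1. Administer the SF-36 to every surviving intervention patient at three months by telephone or post, in one mode for all, whether or not the patient attends the hospital.
2. Use one anchor, either ICU discharge or study inclusion, in all four places that mention the 3-month contact.
3. Let this contact run past the end of the data collection window, and amend the two statements that end follow-up there.
4. Report the number of survivors at three months, the number contacted and the number of completed questionnaires.
5. Unless an SF-36 source for the historical group can be named, report the SF-36 as descriptive 3-month status in the intervention group, and do not use it to answer whether the device changes health perception.
6. Report any in-person strength and ultrasound values at three months as descriptive data in attenders.

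The cost is one call or mailing for each of 30 to 35 patients, using a contact route already foreseen, and a follow-up period of up to about three months after the last inclusion or ICU discharge, depending on the anchor chosen. The final SF-36 results would come correspondingly later.

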#### Conventional early mobilization

The comparison group is a historical collective, which also meets the inclusion and exclusion criteria of the study. These patients were early mobilized following the ward routine of the intensive care units conventional early mobilization according to the instructions of the treatment team, consisting of physicians, nurses, and physiotherapists. Conventional early mobilization cannot be precisely defined on the basis of a retrospective study (45, 15). The information used for the study regarding early mobilization and the defined outcome criteria of the patients is taken from the routinely collected data.

#### Robot-assisted early mobilization

Patients included in the study according to the inclusion and exclusion criteria will be mobilized using the robotic system. The aim is to perform a standardized mobilization with verticalization within the first 72 hours after admission to the Intensive Care Unit. If possible, this should be performed twice every day for 20 minutes, with a minimum of ten treatment cycles or for seven days. Treatment characteristics such as timing, intensity, duration, and complications will be documented.

As part of the study, routinely collected personal data and laboratory chemistry data will also be documented. There will be no blood sampling or other invasive procedure as part of the study. The study period begins for the patients after their informed consent shortly before the surgical procedure and ends approximately 3 months after study inclusion with the planned follow-up examination, with the end of the recording period of the study or the death of the patient.

#### LIST OF THE DATA TO BE COLLECTED

All required information collected in routine clinical practice is to be obtained from the patient documentation system (electronic patient record).

#### 8.1. DATA COLLECTION ORGANIZATIONAL FEASIBILITY

As part of organizational feasibility, population-based data will be collected on a weekly basis. These include the following characteristics:

Characteristic	Expression
Number of newly admitted and eligible patients on the anesthesiological intensive care units per week	Count value
Number of patients enrolled in the study per week	Count value
Number of eligible patients not included in the study	Count value
Number of patients for whom the intervention was discontinued 
 
- from patient side
 
- from clinical side
 
	Count value / rate
Adverse events (46) 
 
- patient-related
 
- user-related
 
- technique-related
 
	Count value

In addition, intervention-related data should be collected daily or on each day that early mobilization is performed.

A unique three-digit ID will be assigned to each patient, under which all data will be recorded pseudonymously. The following data is collected for each mobilization:

#### Patient-related data

Three-digit ID	postoperative day
Date	
Consecutive number of mobilizations	
Duration of mobilization	start - end (number of minutes)
Set-up time preparation	Number of minutes
Set-up time postprocessing	Number of minutes
Number of mobilizing professionals	Number
Intervention related data	
Degree of verticalization	Degree between 0 and 70
Number of minutes in the highest degree of verticalization	Number of minutes
Steps per minute	Number
Total steps	Number
Adverse event / premature termination	yes /no (If yes, type of event)
Feasibility assessment by mobilizing professional	7 point Likert scale
Assessment of the mobilizing professional's own physical stress	7 point Likert scale

## 8.2. DATA COLLECTION BEHAVIOUR AND EXPERIENCE OF MOBILIZING PROFESSIONALS

### 1. Survey of stress/motivation and physical strain

- Episodic interviews (47) at least four people per professional group (until data saturation occurs).
  - o Analysis by means of qualitative content analysis (48)
  - o The mobilizing professionals are interviewed about their emotions in the mobilization situation (see appendix for topics of observation)
- Distress thermometer (49) in conjunction with each interview.
  - o Analysis by means of descriptive statistics (49)

